6.3 Premature Discontinuation

Patients have the right to withdraw from this trial at any time (as described in the informed consent document) without prejudice to further care. An investigator may withdraw a patient from the study at any time for any of the following reasons:

- The patient withdraws his/her consent or refuses follow-up evaluations.
- The patient is lost to follow-up and will not attend further study visits.
- The investigator determines that further participation would be detrimental to the patient's health or well-being.
- The patient fails to comply with the study requirements so as to cause harm to self or seriously interfere with the validity of the study results.
- The female patient becomes pregnant during the treatment period. In this case, treatment should be halted and the patient followed until the end of the pregnancy. If a child is born, the infant should be followed through at least 6 months of age.
- At the discretion of the site investigator if he/she feels that it is in the best medical interest of the patient.

Patients withdrawn from the study will have as many of the trial assessments completed as the patient permits including blood tests and lesion evaluations.

7 DESCRIPTION OF STUDY PROCEDURES

7.1 Efficacy Assessments

7.1.1 ***Modified Composite Assessment of Index Lesion Severity (mCAILS)***

mCAILS score will be calculated by assessing the erythema, scaling, plaque elevation and involved surface area using the grading scale shown in [Table 5](#), [Table 6](#), [Table 7](#), and [Table 8](#) for each of the index lesions. Each of the assessments and the total score for each evaluated lesion will be recorded in the Case Report Form (CRF). The total mCAILS score will be calculated by adding the scores of all evaluated lesions together.

Table 5: Composite Assessment of Index Lesion Severity – Erythema

Score	Description
0	No evidence of erythema, possible brown hyperpigmentation
1	*
2	Mild: Light red lesion
3	*
4	Moderate: Red lesion
5	*
6	Severe: Very red lesion
7	*
8	Very severe: Extremely red lesion

* Intermediate intervals 1, 3, 5, and 7 are to serve as mid-points between the defined grades 0, 2, 4, 6, and 8

Table 6: Composite Assessment of Index Lesion Severity – Scaling

Score	Description
0	No evidence of scaling on lesion
1	*
2	Mild: Mainly fine scales: lesion partially covered
3	*
4	Moderate: Somewhat coarser scales: lesion partially covered
5	*
6	Severe: Coarse, thick scales; virtually all of the lesion covered; rough surface
7	*
8	Very severe: Coarse, very thick scales; all of the lesion covered very rough surface

* Intermediate intervals 1, 3, 5, and 7 are to serve as mid-points between the defined grades 0, 2, 4, 6, and 8

Table 7: Composite Assessment of Index Lesion Severity – Plaque Elevation

Score	Description
0	0 mm: No evidence of plaque above normal skin level
1	Mild elevation
2	Moderate elevation
3	Marked elevation

Table 8: Composite Assessment of Index Lesion Severity – Surface Area

Score	Area ^a
0	0 cm ²
1	>0 and ≤4 cm ²
2	>4 and ≤10 cm ²
3	>10 and ≤16 cm ²
4	>16 and ≤25 cm ²
5	>25 and ≤35 cm ²
6	>35 and ≤45 cm ²
7	>45 and ≤55 cm ²
8	>55 and ≤70 cm ²
9	>70 and ≤90 cm ²
10	>90 and ≤110 cm ²
11	>110 and ≤130 cm ²
12	>130 and ≤155 cm ²
13	>155 and ≤180 cm ²
14	>180 and ≤210 cm ²
15	>210 and ≤240 cm ²
16	>240 and ≤270 cm ²
17	>270 and ≤300 cm ²
18	>300 cm ²

^a Longest diameter and the longest diameter perpendicular to this diameter of each index lesion will be measured to the nearest millimeter. The lesion area will be the product of these two diameters

7.1.2 Modified Severity-Weighted Assessment Tool (mSWAT)

The mSWAT is designed to quantify the disease burden associated with CTCL and is based on an estimate of the percent total area of skin involved based on the body surface area (BSA). The types of lesions are weighted by the lesion characteristic (patch, plaque,

or tumor) as shown in **Table 9**. It will be noted in the CRF if any lesions included in the mSWAT table will not be treated.

Table 9: Modified Severity-Weighted Assessment Tool (mSWAT)

Body Region	% BSA ¹ in Body	Assessment of Involvement in Patient's Skin			
		Region	Patch ²	Plaque ³	Tumor ⁴
Head	7%				
Neck	2%				
Anterior trunk	13%				
Arms	8%				
Forearms	6%				
Hands	5%				
Posterior trunk	13%				
Buttocks	5%				
Thighs	19%				
Legs	14%				
Feet	7%				
Groin	1%				
Weighting Factor		x1	x2	x4	
Subtotal lesion BSA x weighting factor					

¹ BSA = body surface area

² Any size lesion without induration or significant elevation above the surrounding uninvolved skin; poikiloderma may be present.

³ Any size lesion that is elevated or indurated; crusting, ulceration, or poikiloderma may be present.

⁴ Any solid or nodular lesion >1 cm in diameter with evidence of deep infiltration in the skin and/or vertical growth.

7.1.3 The Physician Global Assessment (PGA)

The PGA represents the investigator's assessment of the overall extent of improvement or worsening of the patient's cutaneous disease compared with Baseline as shown in **Table 10**. This assessment is designed to consider ***all cutaneous lesions***, including both index and non-index lesions.

Table 10: Physician's Global Assessment

Grade	Description
0 completely clear	No evidence of disease; 100% improvement
1 almost clear	Very obvious improvement ($\geq 90\%$ to $< 100\%$); only traces of disease remain
2 marked improvement	Significant improvement ($\geq 50\%$ to $< 90\%$ clear); some evidence of disease remains
3 moderate improvement	Intermediate between marked and mild ($\geq 25\%$ to $< 50\%$)
4 slight improvement	$\geq 10\%$ to $< 25\%$; significant evidence of disease remains
5 no change	Disease has not changed significantly from Baseline (10 to -25%)
6 condition worse	Disease is worse than Baseline by $\geq 25\%$

7.2 Safety Assessments

7.2.1 Dermatologic Assessment Grading

For patients randomized to the HyBryte treatment arm, immediately prior to and approximately 10 to 30 minutes after the completion of light therapy, treated lesions and surrounding areas will be graded for erythema, pain, pruritus, edema, hyperpigmentation, hypopigmentation, rash, and vesiculation, with the average score recorded. The reaction will be graded using the definitions in [Table 4](#).

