
Methodology: This will be an open-label trial enrolling patients with CTCL (stage IA, IB, or IIA) randomized to receive topical HyBryte or topical Valchlor for 12 weeks.
 
Patients randomized to HyBryte will apply the drug to all accessible lesions twice per week followed by visible light treatment 21 (± 3) hours later starting at 6 J/cm² and titrated up at each visit until there is evidence of mild erythema of the treated lesions following the light session (Grade 1 erythema on the Erythema Score) and dropping the light dose if there is Grade 2 erythema. Should the patient have Grade ≥ 3, treatment will be suspended for 1 week and treatment may be restarted at a 1 J/cm² lower than the last well-tolerated light dose.
 
Patients randomized to Valchlor will receive commercially available drug applied as per the package insert.
 
Three to 5 prospectively identified index lesions will be evaluated for mCAILS assessment and the lesions chosen will be representative of the patient's overall disease and, if the patient has both patch and plaque lesions, the index lesions should include each type in the approximate same percentage as their total lesions.
 
Patients will be treated for a total of 12 weeks, with follow-up visits at Week 13, Week 14, and Week 16/End of Study. Every three weeks, patients will come to the clinic for an assessment visit (ie, at Week 3, Week 6, Week 9, and Week 12). At these evaluation visits, a cumulative mCAILS, modified Severity-Weighted Assessment Tool (mSWAT), Physician Global Assessment (PGA), Skin Adverse Event Questionnaire (SAEQ) will be completed, and Scoring Dermatitis (SCORD) collected.
 
For HyBryte patients, these assessments will be done immediately prior to light treatment at the second light treatment visit of the evaluation week (ie, Weeks 3, 6, 9, 12).
 
Follow-up assessments will be conducted at Week 13 (1-week post-treatment), Week 14 (2 weeks post-treatment), and Week 16/End of Study (4 weeks post-treatment) and will also include mCAILS, mSWAT, PGA, SAEQ, and SCORD assessments.
 
Physical examinations and safety labs (hematology and chemistry) will be analyzed at Baseline, at the Week 12 assessment visit, and 4 weeks after completion of therapy (Week 16/End of Study). AE's will be recorded throughout the study. Vital signs will be collected at Baseline and Weeks 3, 6, 9, 12, 13, 14 and 16.
		

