4.2 Schedule of Assessments

Patients randomized to receive HyBryte will have assessments and treatment as shown in [Table 2](#).

Table 2: HyBryte Patients: Schedule of Assessments

Activity	Screen	Base-line	Week														
			1	2	3	4	5	6	7	8	9	10	11	12	13	14	16
Clinic visit	X	X	XX	XX	XX	XX	XX	XX	XX	XX	XX	XX	XX	XX	X	X	X
Drug Treatment ^a		X	X	XX													
Informed consent	X																
Entry criteria	X	X															
Medical history	X	X															
Serum HCG (females only)	X	X												X			
Identify index lesions		X															
Interim medical history/AEs			X	X	X	X	X	X	X	X	X	X	X	X	X	X	X
Efficacy assessments ^b		X			X			X			X			X	X	X	X
Safety assessments ^c		X			X			X			X			X	X	X	X
Vital signs		X			X			X			X			X	X	X	X
Physical Exam		X												X			X
Labs ^d		X												X			X

^a Patients will apply HyBryte and come in to clinic 21 ± 3 hours later for light treatments. applications will be done at home twice per week at least 2 calendar days apart except for the second treatment in Weeks 3, 6, 9, and 12 when application should occur following the assessment visit either in the clinic or at home. Patients will have erythema assessment and a dermatologic grading of treated areas before and 10-30 minutes after completion of the light treatment.

^b Efficacy assessments are: mCAILS, mSWAT, PGA

^c Safety Assessments are: SAEQ, SCORD, and collection of AEs

^d Labs are: Clinical hematology panel, Clinical Chemistry panel

Patients randomized to receive Valchlor will be treated as per the Package Insert and will apply a thin film of Valchlor on lesions daily. The Schedule of Assessments for this arm of the study is shown in [Table 3](#).

Table 3: Valchlor Patients: Schedule of Assessments

Activity	Screen	Base-line	Week					
			3	6	9	12	13	14
Clinic visit	X	X	X	X	X	X	X	X
Informed consent	X							
Entry criteria	X	X						
Medical history	X	X						
Serum HCG (females only)	X	X				X		
Identify index lesions		X						
Interim medical history/AEs			X	X	X	X	X	X
Efficacy assessments ^a		X	X	X	X	X	X	X
Safety assessments ^b		X	X	X	X	X	X	X
Vital signs		X	X	X	X	X	X	X
Physical Exam		X				X		X
Labs ^c		X				X		X

^a Efficacy assessments are: mCAILS, mSWAT, PGA

^b Safety Assessments are: SAEQ, SCORD, and collection of AEs

^c Labs are: Clinical hematology panel, Clinical Chemistry panel

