6 STUDY CONDUCT

6.1 General Instructions

This is a pilot, randomized, open-label, active comparator, US, single-center trial in which patients will be randomized to receive HyBryte or Valchlor in a 1:1 randomization. Patients will be treated for 12 weeks and follow-up visits will be conducted 1, 2, and 4 weeks after completion of the treatment phase of the trial.

Patients randomized to HyBryte will have HyBryte applied twice weekly and an opaque covering applied for 21 (± 3) hours followed by the administration of visible light encompassing wavelengths of 500 to 650 nm. The light will be administered with a precisely calibrated device with a light dose starting at 6 J/cm² twice weekly that is titrated up according to the physician's discretion on subsequent sessions, limited by occurrence of Grade 2 erythema or greater but targeting a mild, Grade 1 reaction immediately following the light treatment. All of the patient's lesions that are readily available for exposure to the visible light source will be treated.

Patients randomized to Valchlor will apply a thin film of Valchlor gel once daily to affected areas of the skin and the dosing will follow the instructions for use in the package insert.

Prior to randomization, each patient will have at least 3 and up to 5 index lesions identified. These lesions should be representative of the patient's treated lesions and, if the patient has both plaque and patch lesions, include approximately the same distribution as the patient's other lesions.

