6.2.2 Baseline

At the Baseline visit, the following will be done prior to randomization:

- Confirmation that the patient meets all inclusion/exclusion criteria
- History of any medical changes obtained
- Women of child-bearing potential will have a serum pregnancy test obtained unless the screening test was obtained 7 days or less
- Physical exam
- Vital signs obtained
- Blood for the hematology panel obtained
- Blood for the clinical chemistry panel obtained
- Three to five lesions that are representative of the patient's disease and are discrete with defined borders, will be chosen as the index lesions, and classified as patch or plaque lesions
- Charting of all CTCL lesions on the "Body Lesion Diagram" ([APPENDIX III – Body Lesion Diagram](#)) locating and numbering each of the index lesions
- Each index lesion will have an mCAILS score assessed and recorded
- The mSWAT score will be assessed and recorded
- The SAEQ score will be collected and recorded
- The SCORD score will be collected and recorded

Once all of these assessments are completed, the patient will be randomized into one of the two treatment arms, to receive HyBryte or Valchlor as the study drug. Patients who are randomized into the HyBryte treatment arm will follow the assessments outlined in Section [6.2.3](#). Patients who are randomized into the Valchlor treatment arm will follow the assessments outlined in Section [6.2.4](#).

6.2.3 *HyBryte Patients*

Patients who are randomized into the HyBryte treatment arm will be given a jar of ointment at the Baseline visit. They will be instructed on proper drug application and demonstrate proficiency in drug application and all accessible lesions will be treated with study drug.

6.2.3.1 *Standard light treatment clinic visits*

Patients randomized to HyBryte will have HyBryte applied twice weekly and an opaque covering applied for 21 (± 3) hours followed by the administration of visible light encompassing wavelengths of 500 to 650 nm. The light will be administered with a precisely calibrated device with a light dose starting at 6 J/cm² twice weekly that is titrated up according to the physician's discretion on subsequent sessions. Treatment will target a post-light treatment Erythema score of 1. The light dose will be reduced, maintained or treatment administrations may be suspended if a Grade 2 or greater erythema is present. Additional assessments of treated lesions and surrounding areas will include:

- Erythema
- Pain
- Pruritus

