9.3 Severity of Adverse Event

A clinical determination of the intensity of an AE should be done for all reported AEs. The severity assessment for AEs should be completed using the following definitions as guidelines:

Mild: Awareness of sign or symptom, but easily tolerated.

Moderate: Discomfort enough to cause interference with usual activity.

Severe: Incapacitating with inability to work or do usual activity.

Not applicable: In some cases, an AE may be an “all or nothing” finding, which cannot be graded.

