9.4 Recording Adverse Events

All AEs, whether judged to be related or not to the study drug, should be recorded in both the medical record and the CRF. If photographic evidence is available and relevant, it may be recorded. The start and resolution dates, the judgment of the severity of the AE, the judgment of the relationship of the AE to the study drug, the action taken for subsequent dose of study drug, and the outcome should be noted.

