13 RECORDS MANAGEMENT

13.1 Source Documentation

Original source documents include all informed consent forms, laboratory reports, progress notes, medical histories, physical and diagnostic findings, diagnoses and dates of therapy prior to and during this study, drug dispensing/disposition records which are used to support the data recorded CRFs of each subject. When possible, all data should be documented in an original source document and copied into the CRF.

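### Section 7.2.1 records HyBryte skin reactions as an undefined average with no highest grade, so the entry can show about the target grade when one lesion exceeded it

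*Combined protocol and SAP*

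**What the plan says.** Section 7.2.1 applies to the HyBryte arm only. Treated lesions and the skin around them are graded for eight signs just before light and again 10 to 30 minutes afterwards, on Table 4 (whole grades 0 to IV). The list of signs ends "hypopigmentation, rash, and vesiculation, with the average score recorded". The section gives no unit of averaging and no rounding rule, and asks for no highest grade. Sections 6.2.3.1 to 6.2.3.3 list the same assessment and add none of these.

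The light-dose rules are written as erythema grades:

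- Section 6.1: titration is "limited by occurrence of Grade 2 erythema or greater but targeting a mild, Grade 1 reaction".
- Section 6.2.3.1: the dose may be reduced or maintained, or "treatment administrations may be suspended if a Grade 2 or greater erythema is present".
- Synopsis, Methodology: Grade 2 lowers the light dose, and "Should the patient have Grade ≥ 3, treatment will be suspended for 1 week".

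Table 2, footnote a, appears to name erythema separately: "Patients will have erythema assessment and a dermatologic grading of treated areas before and 10-30 minutes after". No scale or recording rule is given for a separate erythema assessment.

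By contrast, the SCORD worksheet (Appendix II) does define its average: affected lesions, finding by finding.

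**The concern.** A threshold rule asks whether any reaction reached a given grade. An average answers a different question, and it falls as more mildly affected lesions enter the denominator. Where lesions differ, the entry can sit at or near Grade 1 although one lesion reached Grade 2 or 3. Anyone reading the data later could not tell from this entry whether a limit was crossed, or why the light dose was raised, held or cut.

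A preliminary safety comparison is one of the study's objectives (Section 2), and the pilot is meant to expose practical problems before a larger trial (Section 3). Post-light erythema is the signal that limits the light dose. A highest grade that was not written down at the session may not be recoverable afterwards. Section 3 also leaves this grading off its list of safety variables, so how it will be reported is not stated.

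**Working it through.** The plan gives no figure to reproduce. The check is what the entry would show for a known pattern of lesion grades.

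**Inputs from the protocol.** Table 4 grades 0 to IV. At least 3 treatable lesions per patient (Section 5.2), with no upper limit stated. 24 light sessions (Section 4.1). About 10 patients randomized 1:1 (Section 5.1), so about 5 on HyBryte.

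**Assumptions.** Lesion counts of 5 and 10, and the grades at the other lesions. The documents give no lesion-to-lesion variation.

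**One reacting lesion.** For one sign over n lesions, with one at grade g and the rest at grade b:

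mean = (g + (n − 1)b) / n

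| Pattern | n = 3 | n = 5 | n = 10 |
|---|---|---|---|
| one III, others I | 5/3 = 1.67 | 7/5 = 1.4 | 12/10 = 1.2 |
| same, rounded to a whole grade | 2 | 1 | 1 |
| one II, others I | 4/3 = 1.33 | 6/5 = 1.2 | 11/10 = 1.1 |
| same, rounded | 1 | 1 | 1 |
| one III, others 0, all lesions averaged | 3/3 = 1.0 | 3/5 = 0.6 | 3/10 = 0.3 |
| one III, others 0, affected lesions only (as in SCORD) | 3 | 3 | 3 |

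The last two rows describe the same skin. The entry runs from 0.3 to 3 depending on the number of lesions and on which of two sensible conventions is used.

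**How many lesions must react.** With k lesions at III and the rest at I, mean = 1 + 2k/n.

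- The mean reaches 2 when k ≥ n/2: 2 of 3, 3 of 5 or 5 of 10 lesions.
- It rounds to III when the mean is at least 2.5, so k ≥ 0.75n: 3 of 3, 4 of 5 or 8 of 10 lesions.

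**When nothing is lost.** If every lesion has grade g, the mean is g.

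**Volume.** 24 × about 5 = about 120 planned post-light gradings.

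**Other records that might hold the missing grade.**

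- *Adverse events.* Section 9.1.1 covers unintended signs seen by the investigator. Section 9.1.2 counts a new examination finding as treatment-emergent if it requires an intervention, including a change to the prescribed treatment. Events are documented at every light visit (Section 6.2.3.1), and under Section 9.4 "the action taken for subsequent dose of study drug, and the outcome should be noted". But severity is graded by function: severe is "Incapacitating with inability to work or do usual activity" (Section 9.3). That is not the Table 4 grade.
- *SAEQ.* It asks about the worst treated area, but during treatment it is taken before light at Weeks 3, 6, 9 and 12, which is 4 of 24 sessions, and looks back 24 hours. Sessions are at least 2 calendar days apart, so it does not capture the reaction 10 to 30 minutes after light.
- *SCORD.* During treatment it is also taken before light, and its severity items are averages.
- *Source notes.* Section 13.1 lists "progress notes, medical histories, physical and diagnostic findings", and the monitor compares source with CRF (Section 14.1.3). No text requires a grade for each lesion.

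**The case against.** The strongest reply is that this is a documentation gap and not a patient-protection problem. That stands. The dose rules act on erythema that is present, the investigator inspects the skin at every session, and nothing ties dosing to the averaged entry. A reader might infer that severe reactions would go unseen or that titration is unsafe; the documents do not support that.

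A reader might also infer that a Grade 2 or 3 reaction has no route into the adverse event record. That is too strong. The intended reaction is Grade 1, so a higher one can be read as unintended under Section 9.1.1. A lowered or suspended light dose is arguably a change to prescribed treatment under Section 9.1.2. Two limits remain. The route assumes that the skin grading counts as an examination finding. And Section 6.2.3.1 allows the dose to be maintained at Grade 2, so that case may not be captured.

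The average could also be read as running across the eight signs, which would dilute even a uniform Grade III erythema. This reading is strained: Section 6.2.3.1 grades each assessment separately on Table 4, and a mean of pain, hypopigmentation and erythema has no meaning on that scale. Nothing here relies on it.

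Finally, this is a single center that can settle one convention, the output is descriptive with individual listings, and the CRF is not among the public documents and may hold more detail. All fair. But listings can show only what was entered, and a convention settled at the site still would not preserve the highest grade unless it asked for it.

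**Conclusion.** The point holds as a cheap improvement, minor in scale. As written, Section 7.2.1 leaves the average undefined and does not require the highest grade. Under the natural reading, per sign across lesions, the entry can show roughly the target grade when one lesion reached Grade 2 or 3. The adverse event route may catch reactions that change the dose, but without the Table 4 grade.

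The size of the problem is not known. It would be wrong to treat all of the roughly 120 planned post-light gradings as affected: only those where lesions react unequally could be masked, and the documents do not say how common that is. The illustrative averages rest on the assumed lesion counts and background grades. The wording gap itself is certain as far as the protocol text goes. The consequence is confined to one arm of about 5 patients with descriptive reporting.

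**What to change.** In Section 7.2.1 and the CRF:

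1. Define the average as per sign, across treated lesions.
2. Beside it, record the highest grade at any treated lesion, before light and 10 to 30 minutes after, together with the light dose given. Do this at minimum for erythema.
3. Include that highest grade in the HyBryte safety listings.

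In the one-lesion patterns above, the highest-grade field would read 2 or 3 whatever the number of lesions, and so could be set directly against the dose limits. Whether the worst lesion should govern dosing stays with the sponsor and the investigator.

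The cost is a one-line definition and one extra field at each grading (one per sign if all eight are covered), taken from an inspection already done at every session. The downside is that reported grades will look less favourable than averages.
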